8.6 Termination Criteria

A clotting rate of 10% on the Hemoscreen will result in the early termination of the study. The study will run until we have collected 30 suitable samples. Once we have the data from 30 samples the trial will close

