4. BACKGROUND AND RATIONALE

Performing a full blood count (FBC) is a common clinical practice in neonatal care. Samples reported as “clotted” are not able to be analysed and require redraw. A perceived “high” clotting rate elicits frustration among clinical team members and has negative effects on patient flow and patient satisfaction. The overall % rejection rate of neonatal FBC samples due to the presence of clots is high and has been estimated at 20-30% by the neighbouring neonatal units in large teaching hospitals in the region. The literature confirms clotting rejection rate of 30%.¹ Capillary blood is the main technique used to collect blood from neonates. Typically, platelet activation is triggered when there is a break in the vascular endothelium (heel prick). There are studies indicate that capillary blood sampling collection increases the risk of clotting.² There were preliminary evidence show that venous samples have a lower clotting rate but the latter is not an option except in few PICU cases. There are few postulated mechanisms for the cause of clotting in neonates such as the sample transfer time to the laboratory, the blood collection technique, prematurity, neonate weight or coexisting maternal or neonate’s clinical conditions. A recent study demonstrated that a child's increasing body weight reduced the risk of pre-analytical errors, including risk of clotting.² Therefore, the clotting rate is not a large pre-analytical problem in neonates older than 3 months old. However, to date, there are no studies to elucidate the main reason for the high clotting rate in neonates.

There has been ongoing audit work undertaken to establish the exact cause of why these samples seem to be clotting. Sampling technique and a change in blood collection bottles have been considered and implemented but with no clear consistent root cause being identified.³

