5.2 Secondary Objectives

To determine whether the device could offer a solution for the clinical issue of clotted samples from this population group.

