7.3 Sample Collection

The sample collection, analysis and storage is outlined below:

1. When the patient's clinical care requires a FBC result, the sample will be collected with from the baby's heel (capillary) or as a venous sample into a purple topped paediatric EDTA tube. The standard quantity that is collected for this analysis is 400µL.
2. The sample will then be mixed to ensure dispersion of the EDTA anticoagulant through the blood and to ensure an even distribution of blood products. From this sample, 40µL will be drawn from the blood that has collected from the lid of the sample into the HemoScreen capillary sample collection device. The sample collection device will be placed into the HemoScreen cartridge and processed on the analyser by a trained user.
3. The FBC and 5 part differential results will be stored on the analyser and collected by the principal investigator. The clinical team will not report or act on these results.
4. The remaining sample will be labelled up and sent to the laboratory with a request card for FBC analysis.
5. The Laboratory sample will be processed as usual on the Sysmex XN1000 for FBC including 5 part differential.
6. The results will be reported to the clinical team for clinical management. The EDTA sample will be stored in the laboratory for a few days and then disposed as per normal laboratory procedure.

7. The laboratory results will be statistically compared to the retrieved results from HemoScreen (using Altman Bland and Passing Bablock Regression).

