8.5 Successful Criteria

The comparison will be considered successful if a minimum of 95% of HemoScreen results for all parameters are within 2SD (Standard Deviations) from the Laboratory (Sysmex XN1000).

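### The clotting objective has no within-study comparison: the named analyses use only tubes with a result on both analysers, 'suitable' is undefined, and the one clotting rule lacks a denominator and a laboratory comparator

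*Protocol*

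**What the plan says.** - **Objective.** Protocol Section 5.2 gives the secondary objective as "To determine whether the device could offer a solution for the clinical issue of clotted samples from this population group".
- **End of collection.** Section 8.6 states "The study will run until we have collected 30 suitable samples" and then "Once we have the data from 30 samples the trial will close". No section defines 'suitable'.
- **Analyses.** Section 7.3 compares the laboratory and HemoScreen results "using Altman Bland and Passing Bablock Regression". Section 8.5 calls the comparison successful if "a minimum of 95% of HemoScreen results for all parameters are within 2SD (Standard Deviations) from the Laboratory". Neither has a clotting element.
- **Clotted tubes.** Section 4 says that clotted samples "are not able to be analysed and require redraw". It also says that the rejection rate for clots "has been estimated at 20-30% by the neighbouring neonatal units in large teaching hospitals in the region", and cites a literature figure of 30%.
- **Clotting rule.** Section 8.6 stops the study early if the HemoScreen clotting rate is 10%. It does not say 10% of what, after how many tubes, or how this relates to clotting in the laboratory.
- **Sampling.** In Section 7.3 one EDTA tube feeds both analysers. After mixing, 40 µL "will be drawn from the blood that has collected from the lid of the sample" for HemoScreen, and the rest goes to the laboratory.
- **Target.** Section 7.4 sets minimums of 15 babies and 30 samples, with at most two samples per baby.

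**The concern.** Clotting is the clinical problem that motivates the study, and the tubes most informative about it are those that clot in the laboratory. These have no Sysmex value, so they cannot contribute to a Bland-Altman plot, a Passing-Bablok fit or the 2SD criterion. Among tubes with two numeric results, the observed clotting rate is zero on both analysers whatever the true rates are.

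The clotting question then rests on the HemoScreen rate alone, set against a figure from other hospitals. That comparison is not like for like: the external rate comes from large teaching hospitals, whereas study tubes come from one special care unit and are mixed and sampled at the bedside before dispatch. A statement that the device reduces clotting would have no internal control, although one tube feeding both analysers could provide it.

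**Working it through.** **The plan's own figure.** There is none for clotting. The only sample-size figure, ±0.34S in Section 7.4, concerns the differences between methods. At n = 30 the usual formulas give 1.96/√30 = 0.36S for the mean difference and 1.96·√(3/30) = 0.62S for a limit of agreement. That mismatch is a separate matter and does not bear on this point.

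**Inputs.** Laboratory clotting rate p = 0.20 to 0.30 (Section 4); 30 samples and at most two per baby (Sections 7.4 and 8.6). The device clotting rate is not given and is assumed to be 0 to 10%. Tubes are treated as independent.

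**Step 1: 'suitable' means a numeric pair.** Expected tubes = 30/(1 − p); expected clotted = 30p/(1 − p). Only laboratory clots are counted here; HemoScreen failures on other tubes would add to the total.

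| p | Tubes needed | Laboratory-clotted (95% range) | Chance of no clotted tube, (1 − p)^30 |
|---|---|---|---|
| 0.20 | 30/0.8 = 37.5 | 7.5 (2 to 14) | 0.8^30 = 0.1% |
| 0.30 | 30/0.7 = 42.9 | 12.9 (5 to 22) | 0.7^30 = 0.002% |

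At two tubes per baby, with clotted tubes counting towards the two, this is 37.5/2 ≈ 19 to 42.9/2 ≈ 22 babies, against the stated minimum of 15.

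**Step 2: clotted tubes count towards the 30.** The pairs left are 30 × 0.8 = 24 or 30 × 0.7 = 21.

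**Step 3: can the 10% rule stand in for a comparison?**
- The denominator matters. Three HemoScreen clots are 3/30 = 10% against 30 suitable samples, but 3/33 = 9.1% if those three tubes are added to the denominator.
- With 0 clots in 30, the exact 95% upper limit is 1 − 0.025^(1/30) = 11.6%.
- Three or more clots in 30 occur with probability 19% at a true rate of 5% and 59% at a true rate of 10%.

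The rule is therefore imprecise for the device alone, and it says nothing about laboratory clotting of the same tubes.

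**Step 4: what a count of all tubes would give.** Illustrative laboratory rates are 8/38 = 21% (exact 95% CI 9.6 to 37.3%) and 13/43 = 30% (17.2 to 46.1%). The table gives simulated power of an exact two-sided 5% McNemar test. Ranges span device clots that are independent of laboratory clots and device clots that occur only in laboratory-clotted tubes.

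| Tubes, laboratory rate | Device 0% | Device 5% | Device 10% |
|---|---|---|---|
| 38, 20% | 80% | 37-52% | 14-17% |
| 43, 30% | over 99% | 83-98% | 55-89% |

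At 38 tubes, 20% and 5%, even full overlap gives only 38 × (0.20 − 0.05) = 5.7 expected discordant tubes. Five discordant tubes, all in one direction, give p = 2 × 0.5^5 = 0.0625. Estimation should therefore lead and testing be secondary.

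**The case against.** The strongest reply is that a clotting table is ordinary SAP content and the SAP is not shown. A target of 30 suitable samples does not forbid logging the others. HemoScreen clots must be counted in some way to apply the 10% rule, and the laboratory processes its tubes as usual. The study is a pilot, and the objective asks only whether the device could help. A 10% ceiling against a 20-30% background is at least a prespecified benchmark.

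Much of this stands, and it rules out several stronger readings that a reader might infer:

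- *That clotting information is thrown away.* No section says so.
- *That the protocol excludes clotted tubes from the 30.* The term is undefined, so this is an inference. What follows from the text is narrower: such a tube cannot enter the named analyses.
- *That only clotting during transfer can differ between analysers, because both use one tube.* Section 4 says that the main cause is not established, and the analysers receive different aliquots, so a local clot need not affect both.
- *That a paired test would readily settle the question.* The power figures show that this depends heavily on the assumed rates.

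The reply does not remove the point. The end of collection, the closure rule, the success criterion and the 10% rule are fixed in the protocol. They leave one key term undefined, one rate without a denominator, and the stated objective without a laboratory comparator. A later analysis plan would still need a record of every tube drawn.

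**Conclusion.** The point holds in this limited form: the protocol's stated analyses and rules give no within-study comparison of clotting on the two analysers, so the secondary objective rests on an informal external comparison. With laboratory clotting of 20-30%, about 8 to 13 of 38 to 43 tubes would lie outside the agreement analysis on average, or about 21 to 24 pairs would remain if clotted tubes count towards the 30.

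These sizes assume that the rate from neighbouring units applies at this site and that tubes are independent, although a baby may give two. The power figures also assume the device rates shown.

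The absence of clotted tubes from the agreement analysis is not itself a fault. Any same-tube comparison needs a reference value, and the numeric agreement question is unaffected beyond the number of pairs.

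**What to change.** 1. In Section 8.6, define a suitable sample as a tube with a valid numeric result on both analysers, and say that the definition serves the agreement analysis only.
2. Log every study tube drawn, with clotted or no-result status recorded separately for HemoScreen and Sysmex.
3. State that the HemoScreen clotting rate is calculated over all tubes tested.
4. For the secondary objective, report the 2x2 table of clot status and the paired difference in clot rate with a confidence interval that allows for up to two tubes per baby. Any McNemar test is secondary.
5. For laboratory-clotted tubes, the HemoScreen result may be listed beside the laboratory result of the redraw. This is descriptive only: it is different blood at a different time, so it does not measure agreement.
6. Limit the conclusion to bedside testing from an EDTA tube, since Section 7.3 does not fill the device directly from the heel.
7. In Section 7.4, plan for about 38 to 43 tubes if 30 pairs are wanted, and say whether clotted tubes and redraws count towards the limit of two per baby.

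The cost is a tube log, some protocol wording and one extra table. The clotting comparison needs no additional blood, because the same tube already feeds both analysers.

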5. OBJECTIVES

5.1 Primary Objectives

To ascertain whether the device is suitable for a larger scale CE marking research project to enable clinical use of the device in neonates< 2months of age.

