8.4 Spurious Data

Extreme values “outliers” will be ruled out using Box-Cox statistical test.

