9. QUALITY ASSURANCE PROCEDURES AND SAFETY

The study will be conducted in accordance with the current approved protocol, relevant regulations and procedures. All sample analysis will be undertaken in a UKAS

accredited laboratory. Dedicated storage arrangement will aim to maintain sample quality prior to analysis.

The HemoScreen results cannot be used as an alternate to the laboratory results as they are not available to the medical team; the risk associated with this study have been assessed and minimised. They are as follows:

The clinical staff may be tempted to act upon the results generated instead of following the approved care procedure which is to ignore the results as they are for data collection only. To reduce the risk of this, only trained users have access to the device, only research trained nursing staff (not medics) have access to the device, the option to look results up on the analyser has been removed, the printer has been removed. The results will be stored in the device and can only be accessed and retrieved periodically by the principal investigator. A full risk assessment has been written to ensure these risks are minimised. The HemoScreen device will be labelled as under investigation as long as it is in use for this pilot. All the research nurses involved in this study are GCP trained.

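### HemoScreen runs that fail for reasons other than clotting are topped up and never count against the device, so the comparison can succeed whatever the non-clot failure rate

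*Protocol*

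**What the plan says.** - **Primary objective (Protocol 5.1):** "To ascertain whether the device is suitable for a larger scale CE marking research project", for infants under 2 months. Section 4 says the device has been clinically validated only from 2 months of age.
- **Device-failure limit (Protocol 8.6):** "A clotting rate of 10% on the Hemoscreen will result in the early termination of the study". No other kind of failed run has a limit.
- **Sample count (Protocol 8.6):** "The study will run until we have collected 30 suitable samples", and then "Once we have the data from 30 samples the trial will close". 'Suitable' is not defined, and the number of runs attempted has no ceiling.
- **Success (Protocol 8.5):** "a minimum of 95% of HemoScreen results for all parameters are within 2SD" of the laboratory analyser.
- **Data capture (Protocol 7.3 step 3 and section 9):** "The FBC and 5 part differential results will be stored on the analyser and collected by the principal investigator". The stored results "can only be accessed and retrieved periodically by the principal investigator". Neither section describes a record of started runs and their outcomes.

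**The concern.** Whether an analyser suits a new age group depends on two things: whether it returns a result on that blood, and whether the result agrees with the laboratory. Sections 8.5 and 8.6 test the second. Of the first, they test only clotting. An error, an aborted run or a parameter that the analyser will not report has no place in either rule.

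The two rules reinforce each other. Section 8.6 continues until enough usable samples exist, which fills the gap left by a failed run. Section 8.5 then takes its percentage over what was returned. At stake is the conclusion of the pilot: section 14 makes success the step towards a larger multi-centre validation and CE-marking study, and a high rate of non-clot failures would leave no mark on the figure that defines success.

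**Working it through.** The protocol gives no figure for run failure, so there is none to reproduce. Its one precision figure (section 7.4) concerns differences between paired values and does not enter here.

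**Step 1: what happens to each kind of run under the stated rules**

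- *Clot on the HemoScreen:* counts towards the 10% limit in 8.6.
- *No result, non-clot reason:* no limit applies. It supplies no data, so it cannot be one of the 30 samples with data and another sample is collected. It adds nothing to the 8.5 denominator.
- *Partial or suppressed result:* no limit applies. The protocol does not say whether the sample is among the 30. Either way, the missing value is not a HemoScreen result and stays out of the 8.5 denominator.
- *Result returned but disagreeing:* counts against the device in 8.5.

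**Step 2: runs needed for 30 usable samples**

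Inputs: 30 samples (section 8.6); non-clot failure rate f, not given, assumed to be 10%, 20% or 30%. Expected runs = 30/(1 − f); expected failures = 30f/(1 − f). The 95% range of runs is from the negative binomial distribution with independent runs.

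| f | Expected runs | Expected failures | 95% range of runs |
|---|---|---|---|
| 10% | 30/0.9 = 33.3 | 3.3 | 30 to 38 |
| 20% | 30/0.8 = 37.5 | 7.5 | 32 to 44 |
| 30% | 30/0.7 = 42.9 | 12.9 | 35 to 52 |

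None of these failures triggers a rule in the protocol.

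**Step 3: does the success criterion respond to f?**

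For one parameter with 30 returned results, 95% of 30 is 28.5, so at least 29 must agree. Let q be the true share of returned results within the limit (assumed). Then P(pass) = q³⁰ + 30(1 − q)q²⁹.

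- q = 0.95: 0.215 + 0.339 = 0.55
- q = 0.98: 0.545 + 0.334 = 0.88
- q = 0.99: 0.740 + 0.224 = 0.96

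The failure rate f does not appear in the formula. For a given q, the chance of passing is the same at f = 0 and at f = 30%. This treats samples as independent, although section 7.4 allows two per infant.

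**Step 4: what a run count would show**

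Exact (Clopper–Pearson) 95% intervals for the failure rate when 30 usable samples have been reached:

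- 3 failures in 33 runs: 9.1% (1.9% to 24.3%)
- 8 failures in 38 runs: 21.1% (9.6% to 37.3%)
- 13 failures in 43 runs: 30.2% (17.2% to 46.1%)

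These intervals treat the number of runs as fixed. With stopping at the 30th usable sample, the upper limits are unchanged and the lower limits move by less than half a percentage point. The intervals are wide, but the last would bear on suitability, and the present rules do not ask for it.

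**The case against.** The strongest reply is that much of this is detail for an analysis plan that is not shown: evaluable pairs, flagged parameters and run accountability are often defined there. A method comparison also needs paired values, so conditioning on a returned result is inherent in Bland–Altman and Passing–Bablok work. Section 8.5 speaks of the comparison being successful and does not say that it alone settles the primary objective. Success leads only to a larger study, not to clinical use. And 'suitable' may refer to the specimen, not to the device run.

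Part of this stands. An analysis plan could define missing-value handling, and agreement should be estimated on pairs. But the stopping and success rules are fixed in this protocol, and followed exactly they do not respond to non-clot failure. Even if 'suitable' describes only the specimen, 8.6 still closes on data from 30 samples, and a run with no result supplies none. That the next step is another study limits the harm, but a feasibility pilot is where a completion rate should be measured.

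Three stronger readings are tempting but not supported:

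- *That the protocol replaces partial or suppressed runs.* It is silent on them. Only the replacement of runs with no data follows from 8.6.
- *That failed runs will go unrecorded.* Sections 7.3 and 9 say where results are kept; they do not say that nothing else is kept. A clotting rate needs a count of runs, so some count is implied. How a clot is recognised on the device is not stated either, so some failed runs may already be counted as clots.
- *That suitability will be judged after the values are seen, so that unfavourable pairs are dropped.* The undefined word leaves the timing open, but nothing in the protocol provides for this. Outlier removal under 8.4 is a separate matter.

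**Conclusion.** The point holds for the stated rules. Clotting is the only failure to produce a result that has a limit, runs without data are topped up, and 8.5 is calculated over returned results. The comparison can therefore be declared successful whatever the non-clot failure rate.

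The size is conditional. Failure rates of 10%, 20% and 30% are assumptions, and they imply about 33, 38 and 43 runs for 30 usable samples. A reader might infer that the device does fail often in this age group, or that the result will be biased by a known amount. The documents support neither, because they contain no failure rate. What is shown is that the success figure is blind to such failures, and that no rule requires them to be reported beside it. This should be corrected before sampling begins: it changes what the pilot can conclude and costs little.

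**What to change.** 1. **Section 7.3:** have the operator log every started HemoScreen run as complete, partial or no result, with the reason displayed and no values. This keeps the restriction on access to results in section 9.
2. **Section 8.6:** define 'suitable' from that log and the laboratory receipt, and require the decision before HemoScreen values are downloaded.
3. **Section 8.5:** beside the agreement figure, report the proportion of first runs with complete results over all started runs, with an exact 95% CI. State that the suitability conclusion rests on both.

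Agreement can still be estimated on the available pairs; missing parameters need not be scored as disagreement, which would mix analytical agreement with sampling or operator failure.

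The cost is one log line per tube, wording changes in three sections, and a conclusion that may be less favourable to the device. No extra infants or blood are needed.

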9. QUALITY ASSURANCE PROCEDURES AND SAFETY

The study will be conducted in accordance with the current approved protocol, relevant regulations and procedures. All sample analysis will be undertaken in a UKAS

accredited laboratory. Dedicated storage arrangement will aim to maintain sample quality prior to analysis.

The HemoScreen results cannot be used as an alternate to the laboratory results as they are not available to the medical team; the risk associated with this study have been assessed and minimised. They are as follows:

The clinical staff may be tempted to act upon the results generated instead of following the approved care procedure which is to ignore the results as they are for data collection only. To reduce the risk of this, only trained users have access to the device, only research trained nursing staff (not medics) have access to the device, the option to look results up on the analyser has been removed, the printer has been removed. The results will be stored in the device and can only be accessed and retrieved periodically by the principal investigator. A full risk assessment has been written to ensure these risks are minimised. The HemoScreen device will be labelled as under investigation as long as it is in use for this pilot. All the research nurses involved in this study are GCP trained.

